3.4.1 Primary Efficacy Endpoint

Primary Analysis

The primary efficacy endpoint is the percentage of patients with resolution of NASH without worsening of fibrosis. Patients without a valid Week 52 (or ET, if applicable) liver biopsy will be imputed as non-responders. The number and percentage of patients meeting the criteria for the primary endpoint will be summarized by treatment group.

The analysis of the primary endpoint will be performed using the data from the 600 mg NST-4016 and placebo groups using the Cochran-Mantel-Haenszel test, stratified by baseline biopsy fibrosis score (2 levels: F1 or F2/F3). The Cochran-Mantel-Haenszel test p-values will be reported, along with Odds Ratio and 95% confidence interval. Sample SAS code is below.

Secondary Analyses

The key secondary analysis of the primary endpoint will be conducted using data for the 300 mg NST-4016 and placebo groups, again using the Cochran-Mantel-Haenszel test, stratified by baseline biopsy fibrosis score (2 levels: F1 or F2/F3).

Sensitivity Analyses

A sensitivity analysis for the primary endpoint will be carried out using a logistic regression model with treatment group (300 mg NST-4016, 600mg NST-4016, or placebo) and baseline biopsy fibrosis score (2 levels: F1 or F2/F3) as factors. Pairwise treatment comparisons will be estimated in this model as odds ratios (NST-4016 versus placebo) along with their 95% confidence intervals and p-values. Sample SAS code is below.

Additional sensitivity analyses of the analyses described above, CMH and logistic regression, will be conducted for the primary endpoint replacing the stratification factor of baseline biopsy score with the baseline ballooning score (1 or 2).

3.4.2 Secondary Efficacy Endpoints

Continuous efficacy variables will be summarized using descriptive statistics for the observed data and change and/or percent change from baseline by treatment group and visit as appropriate.

3.4.2.1 Responder analysis

The key secondary efficacy endpoints will be summarized and analyzed as described above for the primary efficacy endpoint.

The analysis of key secondary endpoints will also be tested in a hierarchical order as described in Section 3.1.5.

3.4.2.2 Nonalcoholic fatty liver disease activity score (NAS)

The NAS measures disease changes by scoring features of NASH during therapeutic trials. The total NAS represents the sum of scores for steatosis, lobular inflammation, and ballooning, and ranges from 0 to 8.

The change from baseline to Week 52/ET in NAS and individual histological scores (steatosis, ballooning, inflammation, and fibrosis) and a composite Disease Activity Score of inflammation, ballooning and fibrosis will be analyzed using an analysis of covariance model (ANCOVA). The model will be adjusted for treatment (300 mg NST-4016, 600 mg NST-4016, or placebo), biopsy

fibrosis score (2 levels: F1 or F2/F3), and respective baseline score. Pairwise treatment comparisons between each NST-4016 dose and placebo will be estimated using least square (LS) means, standard errors, 95% confidence intervals, and p-values. Sample SAS code is below.

A sensitivity analysis will also be conducted for the NAS and individual histological scores withi an ANCOVA model replacing the stratification factor of baseline biopsy score with the baseline ballooning score (1 or 2).

3.4.2.3 Liver Enzymes

Liver enzymes are assessed at Screening, Visit 2 (Week 0), Visit 3 (Week 4), Visit 4 (Week 10), Visit 5 (Week 16), Visit 6 (Week 24), Visit 7 (Week 32), Visit 8 (Week 40), Visit 9 (Week 52), Visit 10 (Week 54) and at the ET Visit.

The change and percent change from baseline in AST, ALT, ALP, GGT and total bilirubin at each scheduled visit will be analyzed using a Mixed Model Repeated Measures (MMRM) model, with change (or percent change) from baseline as the dependent variable, adjusting for treatment (300 mg NST-4016, 600 mg NST-4016, or placebo), visit, treatment-by-visit interaction, biopsy fibrosis score (2 levels: F1 or F2/F3); and baseline score. The Restricted Maximum Likelihood (REML) estimation approach will be used with an unstructured covariance matrix. The LS means, standard errors, 95% confidence intervals, and p-values for the pairwise treatment comparisons between each NST-4016 dose and placebo will be estimated for each visit.

At visits where the fasted status of the patient is recorded (Visit 2 (Week 0), Visit 5 (Week 16) and Visit 9 (Week 52)), only samples taken in a fasted state will be included. All results from other visits will be included. An additional analysis will be carried out to include patients who we fasted at all three visits where fasted status is recorded.

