3.1.5 Hypothesis Testing

Given the primary and key secondary endpoints along with 2 active doses, hypothesis testing will be performed in a hierarchical order to preserve the overall Type 1 error.

The 600mg dose will be tested first vs placebo. The primary and the 2 key secondary endpoints will be tested in the order as presented in section 2.3.2. Testing of these 3 endpoints will next move to the 300mg dose arm vs placebo. If during the sequential testing of these 6 hypotheses, a p-value is non-significant (at alpha = 0.05), the remaining (from that point onwards) p-values will be considered nominal and significance cannot be claimed.

No multiplicity adjustments will be applied for other secondary endpoints and exploratory parameters analysis. Since the testing of the other secondary endpoints will not involve any control of Type 1 error, all associated p-values are deemed to be nominal.

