3.4.2.4 Inflammation Marker: hsCRP

High sensitivity C-reactive protein (hsCRP) is measured at Visit 2 (Week 0), Visit 5 (Week 16) and Visit 9 (Week 52)/ET.

To be included in the analysis, the patient must have been in a fasted state at the time of the assessment.

The change and percent change from baseline in hsCRP and the log-transformation will be analyzed using a similar MMRM model as described for the Liver Enzymes.

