3.4.2.5 Fibrosis activity markers: Pro-C3 and ELF Test

Pro-C3 (COBAS) and ELF test are measured at Visit 2 (Week 0), Visit 5 (Week 16) and Visit 9 (Week 52)/ET.

To be included in the analysis, the patient must have been in a fasted state at the time of the assessment.

The change and percent change from baseline in Pro-C3 (COBAS) and ELF will be analyzed using a similar MMRM model as described for the Liver Enzymes.

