3.4.2.6 Measure of insulin resistance and metabolic status: HOMA-IR

HOMA-IR is measured at Visit 2 (Week 0), Visit 5 (Week 16) and Visit 9 (Week 52)/ET.

To be included in the analysis, the patient must have been in a fasted state at the time of the assessment.

The change and percent change from baseline in HOMA-IR will be analyzed using a similar MMRM model as described for the Liver Enzymes.

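### The MMRM lets treatment effects vary by visit but fits one baseline slope for all visits; adding a baseline-by-visit term is a cheap improvement that may recover modest precision at Week 52

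*SAP*

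**What the plan says.** SAP 3.4.2.3 models change and percent change in AST, ALT, ALP, GGT and total bilirubin. The fixed effects are treatment, "visit, treatment-by-visit interaction, biopsy fibrosis score (2 levels: F1 or F2/F3); and baseline score". For the residuals, the REML "estimation approach will be used with an unstructured covariance matrix". Baseline enters as a main effect only.

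The enzyme schedule ends with "Visit 8 (Week 40), Visit 9 (Week 52), Visit 10 (Week 54) and at the ET Visit". Read literally, the model therefore covers eight post-baseline visits (Weeks 4, 10, 16, 24, 32, 40, 52 and 54), or seven if the off-treatment follow-up is left out.

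hsCRP "will be analyzed using a similar MMRM model as described for the Liver Enzymes", and SAP 3.4.2.5 and 3.4.2.6 do the same for Pro-C3, ELF and HOMA-IR. These four have two post-baseline visits; hsCRP, for example, "is measured at Visit 2 (Week 0), Visit 5 (Week 16) and Visit 9 (Week 52)/ET".

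Protocol 9.2.1.4 also names only a baseline score, and it names Week 52 as the time point for the pairwise comparisons. SAP 3.4.2.7 treats MRI-PDFF differently: Weeks 16 and 52 go into separate ANCOVA models, so each visit has its own baseline slope. For the other secondary endpoints, which include all the MMRM endpoints, SAP 3.1.5 says that "all associated p-values are deemed to be nominal".

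**The concern.** A measurement four weeks after baseline usually tracks baseline more closely than one taken a year later. If that holds here, the right baseline adjustment differs by visit, and a common slope settles between the early and late values. At Week 52 the adjustment for chance baseline imbalance is then off, and the part left unmodelled goes into the Week 52 residual variance. An unstructured covariance absorbs that variance, so the standard error stays honest but is larger than it need be.

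The second issue is missing data. SAP 3.1.6 and section 6 replace the protocol's multiple imputation of continuous endpoints with available data only, so the MMRM alone deals with missing serial values. SAP 3.4.2.3 to 3.4.2.6 also drop unfasted samples at Weeks 16 and 52. If the chance of a missing Week 52 value depends on baseline, and does so differently by arm, a wrong Week 52 slope can bias the contrast. This matters most for the ITT repeat, because the mITT Population already requires a Week 52 or ET biopsy.

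**Working it through.** **What the plan provides.** No power, SD or correlation is given for any MMRM endpoint, so there is no figure to reproduce on this point. The 88 per group belongs to the binary primary endpoint. It reproduces (40% against 18%, 80% power, two-sided 0.05: 66 evaluable, and 66/0.75 = 88), but it is used below only to size the simulations.

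**Assumptions.**
- Unit variance at every visit, and absolute change as the outcome.
- Correlation between times s and t is a·exp(−λ|s−t|). The constants are set so that the correlation with baseline is r4 at Week 4 and r52 at Week 52: λ = ln(r4/r52)/48 and a = r4·exp(4λ).

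**Formulas.** The true slope at visit k is b_k = r_k for the raw value, or r_k − 1 for change; differences between slopes are the same either way. The fitted common slope is b_c = (1ᵀWb)/(1ᵀW1). Here W is the inverse of S + (b − b_c)(b − b_c)ᵀ, S is the residual covariance under visit-specific slopes, and b_c is found by iteration. The large-sample variance ratio at Week 52, common slope over visit-specific slope, is

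1 + (b52 − b_c)² / (1 − r52²).

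Example with eight visits and correlation falling from 0.80 to 0.40: b_c = 0.691 and b52 = 0.400. The ratio is 1 + 0.291²/0.84 = 1 + 0.0847/0.84 = 1.101, and √1.101 = 1.049 for the SE.

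| r4 → r52 | Enzymes: b_c | Variance ratio | SE ratio | Two-visit markers: b_c | Variance ratio | SE ratio |
|---|---|---|---|---|---|---|
| 0.70 → 0.70 | 0.700 | 1.000 | 1.000 | 0.700 | 1.000 | 1.000 |
| 0.80 → 0.70 | 0.766 | 1.009 | 1.004 | 0.744 | 1.004 | 1.002 |
| 0.80 → 0.60 | 0.742 | 1.032 | 1.016 | 0.694 | 1.014 | 1.007 |
| 0.80 → 0.50 | 0.718 | 1.063 | 1.031 | 0.640 | 1.026 | 1.013 |
| 0.80 → 0.40 | 0.691 | 1.101 | 1.049 | 0.580 | 1.039 | 1.019 |
| 0.70 → 0.30 | 0.556 | 1.072 | 1.035 | 0.460 | 1.028 | 1.014 |

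Other enzyme scenarios fall in the same range: 0.75 → 0.60 gives 1.015, 0.85 → 0.60 gives 1.058 and 0.85 → 0.50 gives 1.099. Leaving out Week 54 barely changes the result (0.80 → 0.40: 1.105).

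**Meaning for power.** A comparison with 80% power under visit-specific slopes has power Φ(2.802/√ratio − 1.960) under the common slope. That is about 79.7%, 78.8% and 76.1% at ratios 1.009, 1.032 and 1.101.

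**Simulation of the eight-visit model, no true treatment effect.**
- Complete data, 66 per arm, 1,000 runs: variance ratio 0.997 with equal slopes, 1.020 for 0.80 → 0.60 and 1.097 for 0.80 → 0.40. No bias under either model.
- About 25% dropout unrelated to baseline, 88 per arm, 400 runs: 1.041 and 1.142 for the same two declining cases (SE up to about 7% larger, since √1.142 = 1.069). No bias.
- Dropout depending on baseline in opposite directions in the two arms compared (log-odds changing by 1.0 per baseline SD), 88 per arm, 400 runs: Week 52 bias of −0.06 and −0.12 SD with the common slope, against +0.006 and −0.014 with the by-visit term. The Monte Carlo standard error is about 0.007 to 0.008.

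**The case against.** The case for leaving the model alone is substantial. The specified model is valid: with complete data, randomisation keeps the Week 52 contrast unbiased whatever the slope, and the unstructured covariance gives an honest standard error. A single baseline covariate also matches Protocol 9.2.1.4. The loss depends on a drift in the slope that the documents neither show nor exclude, and at Weeks 10 to 24 it is at most 1.6% in variance under the same assumptions. The calculation covers absolute change with equal SDs. It does not cover the percent-change analyses or the log-transformed hsCRP analysis, and the pull of the common slope towards early visits follows from the assumed correlation pattern. All of this stands, and it limits the point to an improvement.

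A reader might go further and infer that the Week 52 comparisons are adjusted with the wrong slope and do lose precision. The documents do not support that: with a flat correlation the ratio is exactly 1.000. Nor does the 10% figure apply to every serial endpoint. It belongs to the enzymes; the four two-visit markers reach about 4%.

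A reader might also infer that any dropout related to baseline biases the treatment contrast. The bias found needed dropout that depended on baseline in opposite directions by arm, a deliberately extreme case. Protocol Appendix E ties its drug-discontinuation criteria to baseline enzyme level, which makes some link between baseline and missing data plausible, but nothing in the documents shows that the link differs by arm.

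**Conclusion.** The point holds as a cheap improvement. The MMRM in SAP 3.4.2.3, reused in 3.4.2.4 to 3.4.2.6, has one baseline slope for all visits, while MRI-PDFF, assessed post-baseline at the same Weeks 16 and 52 as the four markers, gets a slope per visit. The SAP gives no reason for the difference.

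The sizes in the table are for complete data and rest on assumed correlations, equal SDs and absolute change. In the worst case of dropout unrelated to baseline, the enzyme loss was about 14% in variance. Bias in the contrast is a possibility under arm-specific, baseline-related missingness, not a demonstrated fault.

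No error-controlled conclusion depends on this. The primary and key secondary endpoints use the Cochran-Mantel-Haenszel test, the histology scores and MRI-PDFF use ANCOVA, and the nine MMRM endpoints lie outside the testing hierarchy.

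**What to change.** In SAP 3.4.2.3, replace the single baseline-score term with baseline score plus a baseline-by-visit interaction, and state in 3.4.2.4 to 3.4.2.6 that the term carries over. Everything else in the model stays. It would also help to say whether Week 54 is one of the modelled visits, since that sets the number of slopes.

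The cost is one term in the model statement: 7 extra parameters for enzymes with eight visits, 6 with seven, and 1 for each two-visit marker. If the slopes are in fact equal, the simulated price is about 0.3% of variance (1/0.997 = 1.003). The change is best made before database lock; after lock, SAP section 1 requires it to be documented in the CSR as a deviation.

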3.4.2.4 Inflammation Marker: hsCRP

High sensitivity C-reactive protein (hsCRP) is measured at Visit 2 (Week 0), Visit 5 (Week 16) and Visit 9 (Week 52)/ET.

To be included in the analysis, the patient must have been in a fasted state at the time of the assessment.

The change and percent change from baseline in hsCRP and the log-transformation will be analyzed using a similar MMRM model as described for the Liver Enzymes.

3.4.2.5 Fibrosis activity markers: Pro-C3 and ELF Test

Pro-C3 (COBAS) and ELF test are measured at Visit 2 (Week 0), Visit 5 (Week 16) and Visit 9 (Week 52)/ET.

To be included in the analysis, the patient must have been in a fasted state at the time of the assessment.

The change and percent change from baseline in Pro-C3 (COBAS) and ELF will be analyzed using a similar MMRM model as described for the Liver Enzymes.

3.4.2.6 Measure of insulin resistance and metabolic status: HOMA-IR

HOMA-IR is measured at Visit 2 (Week 0), Visit 5 (Week 16) and Visit 9 (Week 52)/ET.

To be included in the analysis, the patient must have been in a fasted state at the time of the assessment.

The change and percent change from baseline in HOMA-IR will be analyzed using a similar MMRM model as described for the Liver Enzymes.

3.4.2.7 MRI-PDFF

Hepatic imaging by MRI will be performed at Screening, Visit 5 (Week 16) and Visit 9 (Week 52)/ET. Images will be assessed centrally for MRI-PDFF.

The change from the baseline to Week 16 and Week 52/ET in MRI-PDFF will be performed using similar ANCOVA models as described above. The change from baseline to Week 16 and Week 52/ET will be analyzed in separate models.

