# 9.2.1 Analysis of Efficacy

The efficacy analysis will be performed on the ITT Population; missing values for continuous endpoints will be imputed using multiple imputation methods.

Baseline will be defined as the value at the Screening Visit for measurements from the liver biopsy and imaging data and as the predose value at Visit 2 (Week 0) for the biomarker data. For other efficacy endpoints, baseline will be defined as the predose value at Visit 2 (Week 0); if this value is missing, then the latest predose value will be used.

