#### 9.2.1.4 Secondary efficacy analysis

Continuous efficacy variables will be summarized using descriptive statistics for the observed data and change and/or percent change from baseline by treatment group and visit as appropriate.

Change from baseline to Week 52 in NAS and individual histological scores will be analyzed in an analysis of covariance model, adjusting for treatment (300 mg NST-4016, 600 mg NST-4016, or placebo), biopsy fibrosis score (2 levels: F1 versus F2 or F3), and respective baseline score. Pairwise treatment comparisons between each NST-4016 dose and placebo will be estimated in this model using least square (LS) means, standard errors, 95% confidence intervals, and p-values. A similar analysis will be carried out for the imaging parameters at Week 16 and Week 52.

Efficacy variables measured at multiple timepoints will be analyzed with Mixed Model Repeated Measures methods, with change (or percent change) from baseline as the dependent variable, adjusting for treatment (300 mg NST-4016, 600 mg NST-4016, or placebo), biopsy fibrosis score (2 levels: F1 versus F2 or F3), and baseline score. Pairwise treatment comparisons between each NST-4016 dose and placebo at Week 52 will be estimated using LS means, standard errors, 95% confidence intervals, and p-values.

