3.1.6 Handling of Dropouts and Missing Data

Date Values

In cases of incomplete dates (e.g., AE, concomitant medication, and medical history start and/or stop dates), the missing component(s) will be assumed as the most conservative value possible. For example, if the start date is incomplete, the first day of the month will be imputed for the missing day and January will be imputed for the missing month. If a stop date is incomplete, the last day of the month will be imputed for the missing day and December will be imputed for the missing month. Incomplete start and stop dates will be listed as collected without imputation.

Date imputation will only be used for computational purposes such as treatment-emergent status. Actual date values, as they appear in the original case report forms (CRFs), will be presented within the data listings.

Non-Date Values

Missing values for the primary endpoint, Week 52 (or at the early termination (ET) visit, if applicable) liver biopsy will be imputed as nonresponders.

All other efficacy and safety data will be used according to availability, with no imputation for missing data.

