6 CHANGES FROM PROTOCOL-SPECIFIED STATISTICAL ANALYSES

The planned changes to the protocol-specified statistical analyses, as detailed in this SAP are:

- Key secondary efficacy endpoints added for different definitions of response fibrosis improvement and resolution of NASH with fibrosis improvement.
- cT1 demoted to exploratory endpoint (from secondary) as there is uncertainty over clinical significance.
- The primary population for all efficacy analysis updated to mITT Population, with all analyses to be repeated for the ITT Population.
- No imputation to be performed for the continuous secondary endpoints.
- ALP added to list of liver enzymes to be analyzed as secondary endpoints.

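### Dropping imputation while keeping separate Week 16 and Week 52 ANCOVAs makes the Week 52/ET MRI-PDFF estimate complete-case; the loss falls mainly on the ITT repeat and is minor

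*SAP*

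**What the plan says.** **Schedule.** SAP 3.4.2.7: "Hepatic imaging by MRI will be performed at Screening, Visit 5 (Week 16) and Visit 9 (Week 52)/ET".

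**Model.** Change in MRI-PDFF is analysed by ANCOVA: "The change from baseline to Week 16 and Week 52/ET will be analyzed in separate models". SAP 3.4.3 applies the same approach to cT1, now exploratory.

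**Missing data.** SAP 3.1.6 imputes non-response for the primary endpoint and then states: "All other efficacy and safety data will be used according to availability, with no imputation for missing data". SAP 6 lists this as a change from the protocol, without a reason: "No imputation to be performed for the continuous secondary endpoints". Protocol 9.2.1 had specified the ITT Population, and that "missing values for continuous endpoints will be imputed using multiple imputation methods".

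**Protocol models.** Protocol 9.2.1.4 describes the ANCOVA for histology scores and adds: "A similar analysis will be carried out for the imaging parameters at Week 16 and Week 52". The next paragraph gives a general rule: "Efficacy variables measured at multiple timepoints will be analyzed with Mixed Model Repeated Measures methods".

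**Comparable markers.** SAP 3.4.2.4 to 3.4.2.6 analyse hsCRP, Pro-C3, ELF and HOMA-IR by MMRM. Each is measured at Week 0, Week 16 and Week 52/ET.

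**Populations and status.** Under SAP 3.4, efficacy is analysed in mITT and repeated in ITT and PP. Under SAP 3.2.3, mITT needs a valid baseline and Week 52/ET biopsy and sets no MRI condition. MRI-PDFF is an other secondary endpoint (SAP 2.3.3), and its p-values are nominal (SAP 3.1.5).

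**The concern.** Under the protocol, imputation was what could bring partly observed patients into the Week 52 imaging ANCOVA. Without it, that model uses only patients with a Week 52/ET scan.

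The same change costs other endpoints less. An MMRM uses a patient's Week 16 value when Week 52 is missing, and is valid if missingness depends on observed values. Histology has no intermediate measurement to borrow from. MRI-PDFF and cT1 do have one, and the Week 52 model does not use it.

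Two things are at stake for the Week 52 contrast: precision, and protection against bias if the Week 16 result affects who is scanned at Week 52 and does so differently by arm. Such loss is foreseeable. The plan allows for 25% dropout, and protocol Appendix G lets Visit 9, but not Visit 5, be replaced by telehealth or home visits. Precision has some value here, because protocol 1.4.1.2 reports no change in liver fat at the interim analysis, and a statement of no change leans on the width of the interval.

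**Working it through.** **1. The plan's own figure.** SAP 2.2.2 gives 88 per arm for the primary endpoint (40% v 18%, 80% power, 25% dropout; two-sided 0.05 from protocol 9.2.1.1). With pooled variance and mean proportion 0.29:

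n = [1.96·√(2·0.29·0.71) + 0.842·√(0.40·0.60 + 0.18·0.82)]² / 0.22² = (1.258 + 0.524)² / 0.0484 ≈ 65.6, so 66 per arm.

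66 / 0.75 = 88, which reproduces the plan (power at 66 per arm is 80.2%). The documents give no sample size, SD or power for MRI-PDFF. What carries over is the planned dropout: 0.25 × 88 = 22 per arm.

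**2. Variance formula.** Take n patients per arm with a Week 16 scan, of whom a share f has no Week 52/ET scan. Let ρ be the correlation of the Week 16 and Week 52 changes given baseline, and σ² the residual variance at Week 52.

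- Week 52-only model: variance of an arm mean = σ² / [n(1 − f)].
- Joint model: (σ²/n)·[ρ² + (1 − ρ²)/(1 − f)].
- Ratio, joint to Week 52-only: ρ²(1 − f) + (1 − ρ²) = **1 − ρ²f**.

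At f = 0 the ratio is 1. For patients who have the Week 52 scan, their Week 16 scan adds essentially nothing to the Week 52 contrast.

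**3. ITT repeat, at the ceiling f = 0.25.** ρ is assumed. Extra patients per arm = 66·(1/ratio − 1).

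| ρ | 1 − ρ²f | CI width ratio | Extra patients per arm |
|---|---|---|---|
| 0.3 | 0.978 | 0.989 | 1.5 |
| 0.5 | 0.938 | 0.968 | 4.4 |
| 0.7 | 0.878 | 0.937 | 9.2 |
| 0.8 | 0.840 | 0.917 | 12.6 |

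Simulation with values missing completely at random (6,000 trials per setting, 88 per arm) gave 0.937, 0.881 and 0.840 for ρ = 0.5, 0.7 and 0.8. At f = 0.10 and ρ = 0.7 the formula gives 0.951.

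The ceiling is reached only if all 25% leave after Week 16 and none has a usable ET scan. Patients who leave before Week 16 add nothing to a joint model.

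**4. Lead mITT analysis.** Only patients with a valid biopsy, a Week 16 scan and no Week 52/ET scan count towards f. The documents give no rate. At an assumed f of 2% to 5% and ρ = 0.7, the ratio runs from 1 − 0.49·0.02 = 0.990 to 1 − 0.49·0.05 = 0.976, so the interval narrows by about 1% at most (√0.976 = 0.988).

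**5. Bias.** No figure follows from the documents. Two assumed mechanisms show the range for the Week 52-only contrast; the joint model was close to unbiased in both.

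- Dropout rising with Week 16 PDFF, more so on active: bias of −0.02 to −0.03 SD.
- Dropout depending on the Week 16 change in opposite directions in the two arms, chosen to be adverse: 0.24 SD (ρ = 0.5) and 0.34 SD (ρ = 0.7).

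**6. Who lacks a Week 52 scan.** SAP 3.1.2 assigns ET visits by day window: Week 16 is Days 92–140 and Week 52 is Days 323–371. An ET scan on Days 141–322 would fall to Week 24, 32 or 40, none of which is an imaging visit, and so would enter neither model. SAP 3.4.2.7 labels the later time point Week 52/ET, which suggests that such a scan counts. Protocol 6.5 requires MRI at ET without the six-month condition that it sets for biopsy, so such scans can exist. The reading chosen changes f.

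**The case against.** The SAP follows the protocol's own imaging model. The sentence on imaging in protocol 9.2.1.4 is more specific than the MMRM rule after it, and SAP 6 openly declares the loss of imputation. In the lead mITT set, patients without a Week 52/ET biopsy are already excluded, and an MMRM within mITT would not bring them back. Biopsy and scan belong to the same visit, so few mITT patients should lack only the scan. Nothing in the documents suggests that dropout depends on liver fat, and the milder bias above is only about 0.13 to 0.22 standard errors (0.018 to 0.031 over 0.8·√(2/66) = 0.139, with residual SD 0.8 from an assumed baseline correlation of 0.6). The endpoint carries nominal p-values only.

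All of this stands, and it sets the priority. It does not remove the point: in the ITT repeat, Week 16 scans already in hand are left out of the Week 52 estimate, and the SAP gives no reason for treating imaging differently from four markers on the same schedule.

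A reader might go further and infer that the SAP moved the other markers to MMRM and left imaging behind. The documents do not support that: the protocol had already planned MMRM for those markers and ANCOVA for imaging. Only the imputation changed.

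**Conclusion.** The point holds as a minor one. With imputation gone, the Week 52/ET MRI-PDFF and cT1 estimates are complete-case and take nothing from the Week 16 scans of patients without a Week 52/ET scan. Those scans still enter the Week 16 model.

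In the ITT repeat, a joint model would cut the Week 52 variance by at most about 6%, 12% or 16% for ρ of 0.5, 0.7 or 0.8. In mITT the cut is probably 1% to 2%. These sizes rest on assumed values of ρ and f; the 25% is an upper limit borrowed from the planned dropout.

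It is tempting to apply the 25% figures to the lead analysis, or to call the estimate biased. The mITT definition rules out the first. The second needs missingness that depends on the Week 16 result and selects differently by arm, which the documents do not show. The primary result, the testing hierarchy and the type I error are unaffected.

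**What to change.** In SAP 3.4.2.7 and 3.4.3, analyse change in MRI-PDFF and cT1 with one MMRM at Weeks 16 and 52/ET: treatment, visit, treatment-by-visit, baseline, baseline-by-visit and fibrosis stratum, with unstructured covariance. Report the contrast at each visit. This matters most in the ITT run. Keep the two ANCOVAs as a check. Restoring the protocol's multiple imputation, with the Week 16 value in the imputation model, would also serve.

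Reconcile the day windows in SAP 3.1.2 with the Week 52/ET label in SAP 3.4.2.7, and state which ET scans enter the Week 52 analysis. The MMRM does not settle this by itself.

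The cost is SAP wording and a small programming change: the liver-enzyme MMRM in SAP 3.4.2.3 needs a baseline-by-visit term. No new data are needed, and the missing-at-random assumption is one the SAP already relies on for the other repeated markers. The change should be made before unblinding; made later, it should be labelled supplementary.
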